5.3 Run-in Procedures

Not applicable.

5.4 Contraindications

Participants should avoid excessive ethanol use (>1 standard drinks/day for women, or >2 standard drinks/day for men).

5.5 Concomitant Medications

While on the study agent, participants should avoid NSAIDs and COX-2 inhibitors. While on the study agent, they should avoid taking anticoagulants, antiplatelet agents, and corticosteroids. Participants should discontinue gingko use while taking the study agent. Participants should avoid taking methotrexate (MTX) while taking the study agent.

All medications (prescription and over-the-counter), vitamin and mineral supplements, and/or herbs taken by the participant will be documented on the concomitant medication CRF and will include: 1) start and stop date, dose and route of administration, and indication. Medications taken for a procedure (e.g., biopsy) should also be included.

5.6 Dose Modification

Individuals who report any GI symptom \geq grade 3, such as dyspepsia or heartburn, will be instructed to discontinue the study medication immediately.

Participants reporting minor upper GI symptoms (dyspepsia or heartburn \leq grade 2) who wish to remain on trial will be instructed to treat symptoms with over-the-counter calcium carbonate and/or magnesium hydroxide based antacids (i.e. Tums®, Rolaids®, Mylanta®, etc.) at the manufacturers recommended dose. If symptoms persist or worsen over the next 3 days while taking antacids (\leq grade 2) and the subject still wishes to remain on trial, they will be instructed to treat symptoms with an over-the-counter proton pump inhibitor (PPI). If symptoms persist or worsen while taking a PPI for more than 3 days then the study agent will be discontinued and the participant will be monitored until symptoms resolve. These symptomatic rescue medications will not be provided to the participants by the study.

Individuals who report the following serious side effects that are possibly, probably, or definitely related to the study agent will be withdrawn from the study:

- Bruising grade 2 or above
- Hearing impairment of any grade
- Tinnitus of any grade
- Nausea grade 2 or worse, or nausea grade 1 that lasts for >5 days

- Vomiting grade 2 or worse, or vomiting grade 1 that lasts for >5 days
- Urine output decrease grade 1 or above
- Urine discoloration grade 1,
- Black/tarry stool,
- Blurred vision grade 1 or above
- Headache grade 3 or above
- Serious allergic reaction to the study agent

Individuals who have one of the following results during the intervention will have the result evaluated immediately (preferably within 1 week) and repeated if the treating physician deems necessary. If the treating physician believes the result is possibly, probably, or definitely related to the study agent, or if the repeated test result remains the same, the individual will be withdrawn from the study.

- Blood hemoglobin<12.0 g/dL (anemia, grade 1)
- Platelet count<150,000/microliter (platelet count decreased, grade 1)
- Aspartate aminotransferase (AST) or alanine aminotransferase (ALT) >1.5 times upper limit of normal (ULN) (AST/ALT increased, grade 1)
- Alkaline phosphatase >1.5 times ULN (alkaline phosphatase increased, grade 1)
- Bilirubin > 1.5 times ULN (blood bilirubin increased, grade 2)
- BUN >40 mg/dL
- eGFR<45 mL/min (chronic kidney failure, grade 2)
- Positive fecal occult blood test

5.7 Adherence/Compliance

5.7.1 Participants will be considered evaluable if they have taken 80% of the prescribed doses.

5.7.2 Participant compliance will be monitored in a variety of ways. Patients will be required to keep a diary documenting drug dosing. Returned pills will be counted.

6. PHARMACEUTICAL INFORMATION

6.1 Aspirin (IND: 130627, Exempt, IND Sponsor: NCI/Division of Cancer Prevention)

Aspirin (325 mg capsules) and placebo will be supplied by NCI, DCP. Aspirin is an odorless white, needle-like crystalline or powdery substance. When exposed to moisture, aspirin hydrolyzes into salicylic and acetic acids, and gives off a vinegary-odor. It is highly lipid soluble and slightly soluble in water. The 325 mg aspirin capsule contains 325 mg aspirin and the following excipients: carnauba wax, cellulose, D&C Yellow #10 Aluminum Lake, FD&C Yellow #6 Aluminum Lake, hypromellose, iron oxides, methacrylic acid copolymer, polysorbate 80, propylene glycol, shellac, sodium lauryl sulfate, starch, titanium dioxide, triacetin.

6.2 Reported Adverse Events and Potential Risks

Aspirin has been associated with gastrointestinal (GI) side effects. GI side effects include stomach pain, heartburn, nausea, vomiting, and gross GI bleeding. Minor upper GI symptoms, such as dyspepsia, are common and can occur anytime during therapy. Aspirin has also been associated with elevated hepatic enzymes, blood urea nitrogen and serum creatinine, hyperkalemia, proteinuria, and prolonged bleeding time.

6.3 Availability

Aspirin and aspirin placebo are investigational agents supplied to investigators by the Division of Cancer Prevention (DCP), NCI.

6.4 Agent Distribution

Agents will only be released by NCI, DCP after documentation of IRB approval of the DCP-approved protocol and consent is provided to DCP and the collection of all Essential Documents is complete (see DCP website for description of Essential Documents).

NCI, DCP-supplied agents may be requested by the Investigator (or their authorized designees) at each Organization. DCP guidelines require that the agent be shipped directly to the institution or site where the agent will be prepared and administered. DCP does not permit the transfer of agents between institutions (unless prior approval from DCP is obtained). DCP does not automatically ship agents; the site must make a request. Agents are requested by completing the DCP Clinical Drug Request form (NIH-986) (to include complete shipping contact information) and faxing or mailing the form to the DCP agent repository contractor:

[name]
MRIGlobal
DCP Repository
[name]
[name]
[contact]
[contact]
Emergency [contact]

6.5 Agent Accountability

The Investigator, or a responsible party designated by the Investigator, must maintain a careful record of the inventory and disposition of all agents received from DCP using the NCI Drug Accountability Record Form (DARF). The Investigator is required to maintain adequate records of receipt, dispensing and final disposition of study agent. This responsibility has been delegated to Vanderbilt Investigational Drug Service pharmacists. Include on receipt record from whom the agent was received and to whom study agent was shipped, date, quantity and batch or lot number. On dispensing record, note quantities and dates study agent was dispensed to and returned by each participant.

6.6 Packaging and Labeling

Aspirin and aspirin placebo will be packaged and labeled by NCI, DCP's Repository Contractor MRIGlobal. Three bottles will be dispensed at Clinic Visit 2. One bottle will be dispensed at Clinic Visit 3. The bottles will include 23 capsules. Bottles will be labeled "Weeks 1-3," "Weeks 4-6," "Weeks 7-9," and Weeks "10-12."

6.7 Storage

Study drug will be stored in a secure location, at controlled room temperature (59° F - 86°F) and under low humidity. The Vanderbilt Investigational Drug Service (VIDS) will be responsible for the storage, preparation all investigational agents, and for maintaining accurate drug storage and dispensing logs.

6.8 Registration/Randomization

In current study, there are three groups, two treatment groups (325 mg aspirin daily and 325 mg aspirin 3-week on/3-week off) and one control group. Individuals assigned to 325 mg aspirin 3-week on/3-week off will take placebo during 3-week off period.

This study will recruit 90 participants with colorectal adenoma. A permuted-block randomization design will be used to allocate the subjects into the treatment/placebo arm, and will be created by the study statistician. Both the subjects and the intervention administering staff will be blinded to assignments.

Procedures

1. A study coordinator must upload into the Northwestern Clinical Trials Management System, a signed and complete informed consent along with HIPAA authorization and a completed eligibility form for each participant identified as eligible to be entered into the study.
2. All participants must be registered in the Northwestern University Robert H. Lurie Comprehensive Cancer Center Clinical Trials Management System (CTMS). Participants must not start protocol treatment prior to registration in the Lurie Cancer Center CTMS.
3. After registration in the CTMS, participants will be assigned a participant identification number.
4. An NCPC Quality Assurance Monitor will submit the following into the REDCap Randomization Information Form: (1) Study Number, (2) Site, (3) Pharmacist Email(s), (4) Participant ID [PID], (5) Participant Initials, and (6) Randomization Date.
5. An Automatic Treatment Assignment Notification email will be sent to the research pharmacist(s) containing: (1) Study Number, (2) Site, (3) Participant ID [PID], (4) Participant Initials, (5) Randomization Date, and (6) Treatment Assignment.
6. The clinical research coordinator(s) will receive a Confirmation of Registration containing the PID via email.

The research pharmacist will dispense the study agent.

The following people will have a copy of the un-blinded randomization log: the study statistician at NU, the Quality Assurance Team at NU, and the Investigational Pharmacist at Vanderbilt. The following people will have access to the REDCap study project containing randomization information: the study statistician at NU and the Quality Assurance Team at NU. The study statistician will set up randomization blocks.

When possible, the study coordinator will notify an NCPC Quality Assurance Monitor and/or send an email to [contact] prior to registering a participant. Prior notification is required for participant randomizations outside the normal business hours of Monday-Friday 9:00am-5:00pm CT.

6.9 Blinding and Unblinding Methods

The research pharmacist will manage the investigational agent. The blind will be maintained through the effort of the research pharmacist and the pharmacy. Unblinding will only occur when it is deemed medically necessary, and will only take place after consultation with the NCI, DCP Task Order Monitor. If the NCI Task Order Monitor cannot be reached and the participant requires emergency care, the Study Chairman may authorize the site PI to break the blind. The date and reason for breaking the blind must be submitted by the site PI to the Study Chairman and the NCI Task Order Monitor as soon as possible.

[name], DO, MSc
National Cancer Institute
Division of Cancer Prevention
Gastrointestinal and Other Cancers Research Group

[name]
[name]
[contact]
Fax (*with cover sheet, Attn: [name]): [contact]
Email: [contact]

6.10 Agent Destruction/Disposal

At the completion of investigation, all unused study agent will be returned to NCI, DCP Repository according to the DCP "Guidelines for AGENT RETURNS" and using the DCP form "Return Drug List".

7. CLINICAL EVALUATIONS AND PROCEDURES

7.1 Schedule of Events

	Clinic Visit 1: Screening	Clinic Visit 2: Baseline, within 6 weeks of Clinic Visit 1	Between-Visit Telephone or Email Contacts	Clinic Visit 3: 9 weeks after start of study agent [6]	Clinic Visit 4: 12 weeks after start of study agent [7]; or Off-Agent Visit [8]
Informed Consent	X				
Eligibility	X				
Registration/Randomization [1]	X				
Collect/Review Questionnaires [2]		X			
Medical History	X				
Physical [13]	X				
Vital Signs [12], Body Measurements [3]	X	X		X	X
Con Med Review	X	X		X	X
Assess Adverse Events	X	X		X	X
Pregnancy Test	X				
Blood Sample for Clinical Labs [10]	X	X		X	X
Blood Sample for Research [11]	X	X		X	X
Urine Sample [9]	X	X		X	X
Stool Sample	X	X		X	X
Rectal Swab		X		X	X
Rectal Biopsies [4]		X		X	X
Dispense Study Agent		X		X	
Collect/Count Unused Pills and Review Participant Diary				X	X
Telephone or Email Contact [5]			X		X [14]
Compensation	X				X

[1] Registration and randomization will occur between Clinic Visit 1 and Clinic Visit 2

[2] Clinic Visit 2: Food Frequency Questionnaire and Baseline Clinic Visit Questionnaire

[3] Height; weight; hip and waist circumferences

[4] Verify empty rectal vault prior to rectal biopsy procedure

[5] Phone or email contacts will include the following topics: compliance, adverse events, reminder to switch bottles, reminder to bring unused pills back to clinic. Participants will be contacted within 3 days after each biopsy visit (after Clinic Visits 2, 3, and 4), and at Weeks 1, 3, and 6 (± 3 days).

[6] Range: 8 weeks – 9 weeks and 2 days (56 – 65 days) after starting the study agent

[7] Range: 11 weeks – 12 weeks and 2 days (77 – 86 days) after starting the study agent

[8] If a participant comes off-agent (e.g. due to AE or concomitant medication), the Off-Agent Visit will be scheduled for as soon as possible after the participant stops the study agent.

[9] Urine samples will be obtained only from participants who agree to future unspecified research in the consent form.

[10] Clinic Visit 1-4: 1 green top tube for CMP and 1 purple top tube for CBC with differential. CMP and CBC will be processed on the day of the visit.

[11] 1 EDTA purple top tube for plasma, white blood cell (WBC), red blood cell (RBC); 1 red top tube for serum.

[12] ECOG performance status obtained at Screening Visit only. Vital signs include pulse, respirator rate, temperature, and blood pressure.

[13] Physical exam may be performed at any follow-up visit when deemed appropriate by study team due to significant changes or medical events.

[14] Follow-up phone call to assess adverse events 1 month \pm 7 days from Clinic Visit 4.

7.2 Pre-study Evaluation

Clinic Visit 1: Screening

- Prior to the visit
 - The research staff will mail the participant a stool collection kit. The participant will collect stool and bring it to the clinic. Participants who fail to bring in the stool sample to the office visit will be asked to try to produce a sample during the clinic visit. If unable, they will be asked to bring or mail the stool sample after Clinic Visit 1 for the fecal occult test.
- During the visit
 - Obtain written informed consent (the study participant will keep a copy).
 - Review medical history, physical including vital signs, ECOG performance status, concomitant medications, and symptoms.
 - Obtain the following specimens:
 - One tube of urine (for optional future research)
 - One tube of stool (brought from home for fecal occult blood test)
 - Two tubes of blood (for clinical laboratory measurements): 1 green top for CMP and 1 purple top for CBC with differential.
 - Two tubes of blood (for research): 1 EDTA purple top for plasma, white blood cell (WBC), red blood cell (RBC); 1 red top for serum.
 - Perform a pregnancy test
- After the visit
 - Research staff will review final inclusion/exclusion criteria based on laboratory results.
 - Participant will be registered in the Northwestern Oncology Trial Information System (NOTIS).
 - Results of the inclusion/exclusion criteria review will be communicated to the participant.

Clinic Visit 2: Baseline

Within 6 weeks of Clinic Visit 1

- Prior to the visit
 - The research staff will mail or give the participant a stool collection kit. The participant will collect stool and bring it to the clinic.
 - The research staff will mail or give the participant the Food Frequency Questionnaire (FFQ) and Baseline Clinic Visit Questionnaire. The participant will complete these questionnaires prior to arriving.
- During the visit
 - Review vital signs, concomitant medications, and symptoms.
 - Physical exam may be performed when deemed appropriate by study team due to significant changes or medical events.
 - Review the FFQ and Baseline Clinic Visit Questionnaire.
 - Obtain the following specimens:
 - One tube of urine (for optional future research)

- One tube of stool (brought from home for fecal occult blood test)
- Two tubes of blood (for clinical laboratory measurements): 1 green top for CMP and 1 purple top for CBC with differential.
- Two tubes of blood (for research): 1 EDTA tube for plasma, white blood cell (WBC), red blood cell (RBC); 1 red top for serum.
- Rectal swabs
- Rectal biopsies
- Dispense first three bottles of study agent and participant diary.
- Give the participant a stool sample collection kit to use prior to Clinic Visit 3.
- After the visit
 - Within 3 days after the visit, the research staff or nurse will telephone or email each participant to monitor for any adverse events due to biospecimen collection as well as compliance monitoring. Suggested statements for participant communications are provided in Appendix E.

7.3 Evaluation During Study Intervention

Between-Visit Telephone or Email Contacts

Weeks 1, 3, and 6 (± 3 days)

The research staff will telephone or email each participant to discuss the following:

- Any adverse events
- Changes in concomitant medications
- Compliance monitoring
- A reminder that, at the beginning of weeks 3 and 6, the participant needs to switch bottles.

The Week 6 Telephone or Email Contact will include the following reminders:

- To bring unused study agent with them to the next Clinic Visit.
- To have a bowel movement prior to their visit, to prepare for the rectal biopsy procedure.

Suggested statements for participant communications are provided in Appendix E.

Clinic Visit 3: 9 Weeks

8 weeks - 9 weeks and 2 days (56 – 65 days) after start of study agent

- Prior to the visit
 - The participant will collect stool using the collection kit given to them during Clinic Visit 2.
- During the visit
 - Review vital signs, concomitant medications, and symptoms.
 - Physical exam may be performed when deemed appropriate by study team due to significant changes or medical events.
 - Obtain the following specimens:
 - One tube of urine (for optional future research)
 - One tube of stool (brought from home for fecal occult blood test)
 - Two tubes of blood (for clinical laboratory measurements): 1 green top for CMP and 1 purple top for CBC with differential.
 - Two tubes of blood (for research): 1 EDTA tube for plasma, white blood cell (WBC), red blood cell (RBC); 1 red top for serum.
 - Rectal swabs
 - Rectal biopsies
 - Collect unused study agent and participant diary and conduct a pill count.
 - Dispense fourth bottle of study agent.
- After the visit

- Within 3 days after the visit, the research staff or nurse will telephone or email each participant to monitor for any adverse events due to biospecimen collection as well as compliance monitoring. Suggested statements for participant communications are provided in Appendix E.

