Clinic Visit 3 (9 weeks after starting study agent): Concomitant medications are reviewed and vital signs are performed. A blood and stool sample are collected for clinical monitoring. Mid-study specimens collected include rectal swabs, and biopsies. An optional urine sample is collected. Unused pills are collected and counted. The fourth bottle of study mediation is dispensed.

Clinic Visit 4 (12 weeks after starting study agent): Concomitant medications are reviewed and vital signs are performed. A blood and stool sample are collected for clinical monitoring. Post-study specimens collected include rectal swabs, and biopsies. An optional urine sample is collected. Unused pills are

collected and counted.

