5.2 Aspirin Administration

The aspirin and matching placebo capsules will be provided by the National Cancer Institute (NCI) and packaged and labeled by NCI Division of Cancer Prevention's repository contractor, MRIGlobal. The Vanderbilt Investigational Drug Service (VIDS) will be responsible for the storage (controlled room temperature 59° F - 86° F and under low humidity), preparation of all investigational agents, and for maintaining accurate drug storage and dispensing logs.

Each participant will receive four bottles:

- Bottle 1 labeled "Weeks 1-3"
- Bottle 2 labeled "Weeks 4-6"
- Bottle 3 labeled "Weeks 7-9"
- Bottle 4 labeled "Weeks 10-12"

Bottles 1-3 will be dispensed at Clinic Visit 2. Bottle 4 will be dispensed at Clinic Visit 3. The prescription (and, for the first dispense, the signed consent form) will be faxed to VIDS. The research staff will transport the capsules from VIDS to the participant at clinic. Participants will be instructed to take study medication with food to decrease the risk of GI upset.

If the participant is unable to stay at the clinic to receive the capsules, the pharmacist at VIDS will mail the capsules via Fedex within one business day of the Clinic Visit. Research staff will follow-up with a phone call to the participant to ensure receipt of study agent.

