7.4 Evaluation at Completion of Study Intervention

Clinic Visit 4: 12 Weeks

11 weeks – 12 weeks and 2 days (77 – 86 days) after start of study agent

OR

Off-Agent Visit

- Prior to the visit
 - The participant will collect stool using the collection kit given to them during Clinic Visit 3.
- During the visit
 - Review vital signs, concomitant medications, and symptoms.
 - Physical exam may be performed when deemed appropriate by study team due to significant changes or medical events.
 - Obtain the following specimens:
 - One tube of urine (for optional future research)
 - One tube of stool (brought from home for fecal occult blood test)
 - Two tubes of blood (for clinical laboratory measurements): 1 green top for CMP and 1 purple top for CBC with differential.
 - Two tubes of blood (for research): 1 EDTA tube for plasma, white blood cell (WBC), red blood cell (RBC); 1 red top for serum.
 - Rectal swabs
 - Rectal biopsies
 - Collect unused study agent and participant diary and conduct a pill count.
- After the visit
 - Within 3 days after the visit, the research staff or nurse will telephone or email each participant to monitor for any adverse events due to biospecimen collection as well as compliance monitoring. Suggested statements for participant communications are provided in Appendix E.

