Appendix D – Participant Diary

Protocol NWU2015-06-01

Participant ID: _____

Instructions: Take once per day with food.

Switch to Bottle 2 (labeled “Weeks 4-6”) starting on Day 22.

Switch to Bottle 3 (labeled “Weeks 7-9”) starting on Day 43.

Switch to Bottle 4 (labeled “Weeks 10-12”) after Clinic Visit 3.

DAY: _____ BOTTLE: _____ DATE: ____ / ____ / ____ TIME: _____ Please list new symptoms, new medications, or reasons for missed doses: _____ _____ _____ _____	DAY: _____ BOTTLE: _____ DATE: ____ / ____ / ____ TIME: _____ Please list new symptoms, new medications, or reasons for missed doses: _____ _____ _____ _____	DAY: _____ BOTTLE: _____ DATE: ____ / ____ / ____ TIME: _____ Please list new symptoms, new medications, or reasons for missed doses: _____ _____ _____ _____	DAY: _____ BOTTLE: _____ DATE: ____ / ____ / ____ TIME: _____ Please list new symptoms, new medications, or reasons for missed doses: _____ _____ _____ _____	DAY: _____ BOTTLE: _____ DATE: ____ / ____ / ____ TIME: _____ Please list new symptoms, new medications, or reasons for missed doses: _____ _____ _____ _____	DAY: _____ BOTTLE: _____ DATE: ____ / ____ / ____ TIME: _____ Please list new symptoms, new medications, or reasons for missed doses: _____ _____ _____ _____	DAY: _____ BOTTLE: _____ DATE: ____ / ____ / ____ TIME: _____ Please list new symptoms, new medications, or reasons for missed doses: _____ _____ _____ _____

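### Bottle 4 start is tied to a floating Visit 3 with no Visit 3–Visit 4 limit, so permitted dates can shorten the Bottle 3 block and exhaust Bottle 4 by the primary biopsy (minor)

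*Combined protocol and SAP*

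**What the plan says.** The first two bottle switches have calendar days. In Appendix D, Bottle 2 starts on Day 22 and Bottle 3 "starting on Day 43". Bottle 4 has none: participants switch to it "after Clinic Visit 3".

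- **Visit 3 window (7.3; also 7.1, note 6):** "8 weeks - 9 weeks and 2 days (56 – 65 days) after start of study agent".
- **Supply (5.2):** "Bottle 4 will be dispensed at Clinic Visit 3". Bottle size (6.6): "The bottles will include 23 capsules".
- **Leftovers at Visit 3 (7.3):** "Collect unused study agent and participant diary and conduct a pill count".
- **Visit 4 window (7.4):** "11 weeks – 12 weeks and 2 days (77 – 86 days) after start of study agent". Section 13.4 takes the primary endpoint as the change from baseline to this visit.

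Both visits are timed from the start of study agent. No section sets an interval between them, and none tells a participant seen early at Visit 3 to finish Bottle 3 first or to keep its capsules.

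Two other places point to a different switch day for early attenders. The Bottle 4 label covers weeks 10 to 12 (5.2, 6.6), which means Day 64 onwards. The suggested message in Appendix E asks for 21 consecutive days per bottle, and lists dates for the first two switches but not for Bottle 4.

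**The concern.** The intervention being compared is a dosing schedule. The primary test asks whether daily and intermittent aspirin are equivalent on the change in Ki-67/BAX to the Visit 4 biopsy, so exposure in the weeks before that biopsy should follow the planned blocks as far as visit windows allow.

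The windows are lopsided: each visit may be 7 days early but only 2 days late. The two spare capsules per bottle cover the late side only. An early Visit 3 ends Bottle 3 early, starts the 23-capsule Bottle 4 early, and leaves Visit 4 where it was. A fully compliant participant can then receive a short Bottle 3 block and also run out of Bottle 4.

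Nothing in the plan would flag this. Section 13.8 bases its efficacy conclusions on all treated eligible participants with enough biopsies, deviations included. The 80% evaluability rule in 5.7.1 is not approached (see the working).

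**Working it through.** **Inputs.** V3 = 56 to 65 (7.1, 7.3); V4 = 77 to 86 (7.1, 7.4); Bottle 3 starts on Day 43 (Appendix D); 23 capsules per bottle (6.6). The stated windows reproduce: 8×7 = 56, 9×7+2 = 65, 11×7 = 77, 12×7+2 = 86. Day n of a visit window is treated as diary Day n.

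**Nominal dates (63 and 84).** Bottle 3 lasts 63 − 42 = 21 days and the interval is 84 − 63 = 21 days, within 23 capsules. There is no shortfall.

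**Bottle 3 block**, first Bottle 4 capsule on the day after Visit 3: days = V3 − 42.
- V3 = 56 gives 14; V3 = 65 gives 23.
- The block is below 21 for V3 = 56 to 62, which is 7 of 10 permitted days, by 1–7 days. Visit 4 has no bearing on this.
- If Bottle 4 starts on the visit day itself, each block is one day shorter.

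**Final interval** = V4 − V3, over 10 × 10 = 100 permitted pairs.
- Range: 77 − 65 = 12 to 86 − 56 = 30.
- Exactly 21 days in 10 pairs, fewer in 45, more in 45.
- More than 23 days in 7+6+5+4+3+2+1 = 28 pairs (V3 = 56, 57, …, 62 respectively). All 28 have an early Visit 3, so all also have a short Bottle 3 block.

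**Capsule-free days before the biopsy day:**

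| First Bottle 4 capsule | Last capsule day | Capsule-free days before V4 | In the 28 pairs |
|---|---|---|---|
| On the visit day | V3 + 22 | V4 − V3 − 23 | 1–7 |
| Day after the visit | V3 + 23 | V4 − V3 − 24 | 0–6; at least 1 in 21 pairs |

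In the second row the other 7 pairs lack a capsule only on the biopsy day. Counted as V4 − V3 − 23, the excess is 3 days or fewer in 7+6+5 = 18 of the 28 pairs, and 7 days in one pair only (V3 = 56, V4 = 86). With Visit 4 on its nominal day 84, an excess appears once Visit 3 is on day 60 or earlier (84 − 60 − 23 = 1).

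**Exposure, next-day start.**
- Daily arm, worst case: 56 + 23 = 79 doses, which is 79/84 = 94.0% of the nominal total or 79/86 = 91.9% of the longest. A visit-day start gives one fewer. Both stay well above 80%.
- Intermittent arm, full compliance, starting with aspirin: 21 + (14 to 23) = 35–44 aspirin days against 42 planned. The last aspirin falls 12–30 days before Visit 4 against 21 planned.

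**Day numbering.** If the windows count elapsed days and the diary counts first dose as Day 1, each visit falls one diary day later. The interval V4 − V3, and so the 28 pairs, do not change.

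**Power.** The stated TOST powers reproduce at n = 32 per arm: 0.519, 0.814 and 0.911 against 0.52, 0.81 and 0.91. They do not depend on visit timing.

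**The case against.** The strongest reply is that this is ordinary visit-window tolerance with no demonstrated consequence. Nominal dates work, power is untouched, worst-case daily-arm intake is above 90%, and most gaps are a few days. All of that stands and sets the severity.

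Existing provisions also help in part. Section 8.3(2) lists lack of agent as an off-agent reason and calls for a prompt Off-Agent Visit. With a next-day start, the last capsule in the 28 pairs falls on days 79–85, inside the Visit 4 window, so that visit could still be in window. But it can be triggered only once supply has run out, and it does nothing for a short Bottle 3 block. Note 5 of 7.1 requires contact within 3 days after Visit 3 and lists bottle switching as a topic, which partly makes up for the missing date in Appendix E. Appendix E contains suggested statements, so it is better described as conflicting guidance than as a second rule.

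Three stronger readings are tempting, and the documents support none of them:

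- **That 28% of participants would run short.** The documents give no distribution of visit dates; 28 of 100 counts permitted pairs.
- **That the trial is biased towards equivalence.** A late gap in the daily arm would make the arms more alike. But the same 28 pairs also shorten the second aspirin block and lengthen the final off block in the intermittent arm, which would separate them. The net direction is unknown.
- **That a week without aspirin before the biopsy is typical.** Seven days arises in one pair, and only with a visit-day start.

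**Conclusion.** The point holds as a minor scheduling gap. Permitted dates can shorten the Bottle 3 block by 1–7 days (7 of 10 Visit 3 days) and, in 28 of 100 date pairs, exhaust Bottle 4 before or on the day of the primary biopsy. No provision prevents this. The effect on Ki-67/BAX cannot be sized from the documents.

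The conclusion rests on three things:

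- **The instructions are followed literally:** Bottle 4 starts on the day of Visit 3 or the next, and leftover capsules are handed back.
- **The intermittent sequence starts with aspirin.** Section 3 names active before placebo, but the order is not stated outright. On this inference Bottle 3 is the second aspirin block and Bottle 4 is placebo, which is why run-out costs aspirin only in the daily arm.
- **The day convention,** which moves the counts by one day, as shown.

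**What to change.** **Core change.** Add to 7.1 and 7.4 that Visit 4 is scheduled no more than 23 days after Visit 3. This is always possible inside the existing window: with Visit 3 on day 56, Visit 4 may be on days 77–79 (3 choices). The choices rise by one per day to 9 at day 62, and all 10 are open from day 63. In total, 72 of 100 pairs remain. It closes the supply gap at the cost of one scheduling line. It does not restore a short Bottle 3 block.

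**To protect the Bottle 3 block as well.** Start Bottle 4 on Day 64 or after Visit 3, whichever is later, and let early attenders keep Bottle 3 through Day 63. This agrees with the bottle label and Appendix E. Give the Bottle 4 start date at the contact after Visit 3. Bottle 3 then lasts 21–23 days, intermittent aspirin days are 42–44, and no pair runs short (64 + 23 − 1 = 86), so the cap is no longer needed for supply. It takes wording changes in Section 3, 7.1, 7.3, Appendix D and Appendix E, with no new visits or capsules.

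Its downsides should be stated:

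- Final blocks under 21 days become more common: (8 × 7) + 8 + 9 = 73 pairs against 45. The minimum is still 12 days, and the mean absolute departure from 21 is unchanged at 3.3 days. What goes away is the 24–30 day final block.
- No capsule is spare for a day-86 Visit 4. If that is diary Day 87, supply ends the day before the biopsy.
- Early attenders briefly hold two bottles, possibly active and placebo in the intermittent arm, so a mix-up would blur the schedule under test. Their Bottle 3 pill count is completed at Visit 4.
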